1.0 Study Summary

Study Title	Pilot Study of Nurse-Administered Touch and Biobehavioral Stress Responses of Preterm Infants (Pilot NAT-BIO Study)
Study Design	Randomized cross-over clinical trial
Primary Objective	Determine the effect of a nurse-administered touch intervention (NaTI) on biobehavioral stress responses of preterm infants during essential nursing care.
Secondary Objective(s)	(2) Identify factors to increase feasibility of the NaTI as a nurse-administered, integrated part of essential, procedural care, (3) Determine associations between biobehavioral responses and early neurobehavior.
Research Intervention(s)/ Investigational Agent(s)	NaTI (NaTI): NaTI is a systematic touch intervention consisting of 3 static, brief touches lasting a total duration of 2.5 minutes provided by bedside nurses at specified points during essential care. The intervention is provided with bare hands (i.e. gloves are not worn).
IND/IDE #	N/A
Study Population	Preterm infants born 27 to 30 weeks post-menstrual age; NICU nurses
Sample Size	Up to 20 infants; up to 20 nurses
Study Duration for individual participants	Infant participation on each of 2 days will last approximately 6 hours from the attachment of electrodes for skin conductance responses and heart rate/heart rate variability to the removal of these electrodes. Infant participation will include data collection on two consecutive days for a total duration of 24-48 hours. Infant neurobehavior will be assessed at 35 weeks post-menstrual age. The assessment takes 20-30 minutes. Total infant participation will last from the time of the first observation to neurobehavioral assessment (approximately 5-7 weeks), depending on anticipated discharge and clinical stability for the neurobehavioral assessment. Nurse participation will last approximately 15 minutes per survey completion.
Study Specific Abbreviations/ Definitions	NaTI: nurse-administered touch intervention SC: standard care NAPI: Neurobehavioral Assessment of the Preterm Infant AIM: Acceptability of Intervention Measure IAM: Intervention Appropriateness Measure FIM: Feasibility of Intervention Measure SID: study-specific identification Observation period: period of active study participation for infants lasting approximately 6 hours and beginning with the attachment of electrodes before the scheduled care episode during which data collection will occur and ending with the following scheduled care episode when electrodes are removed.

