3.0 Background

3.1 Infants born preterm experience neurodevelopmental impairments in cognition³, motor function³, and language acquisition^{4,5}. In the United States, 50% of cerebral palsy cases and 8% of learning disabilities are attributable to preterm birth⁶. While many preterm infants receive early intervention services after neonatal intensive care unit (NICU) discharge, these services are costly and not available to all eligible infants⁷⁻⁹. Interventions during NICU hospitalization may improve neurodevelopment and reduce the human, societal, and economic burdens of neurodevelopmental impairment in preterm infants.

Stress exposure in the NICU is associated with abnormal brain development¹⁰⁻¹² and cognitive, motor, and behavioral neurodevelopmental impairments¹³⁻¹⁶. Preterm infants experience an average of 7.5-17.3 painful procedures¹⁷ and 22.97 acute stressors¹⁶ per day of hospitalization. Seemingly benign procedures (e.g. diaper changes, repositioning) are among the most frequent stressors^{16,18} and are commonly clustered together during essential nursing care. Essential nursing care is a frequent, repeated stressor, typically occurring every 3 or 4 hours during the infant's hospitalization. Most episodes (86%) of essential care begin with an abrupt rather than a gradual approach¹⁸, without time for infants to acclimate. Because essential care is repeated, frequent, and abrupt, interventions targeting how essential care is provided may affect preterm infant stress responses and improve outcomes.

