4.0 Study Endpoints

- 4.1 Data collection to accomplish aims 1 & 2 will last the duration of two observation periods, one each on two consecutive days. Infant participation will last approximately six hours for each observation period. Participation will begin approximately three hours prior to a scheduled care episode (i.e. data collection period) when monitoring electrodes are attached and will end approximately 2.5 hours after the scheduled care episode (i.e. data collection period) when the next care episode begins and study electrodes are removed. Infants will receive a neurobehavioral assessment at approximately 35 weeks PMA. The timing of this assessment will depend on anticipated discharge and clinical stability. Infant participation for the entire study will last between 5-7 weeks, depending on infant PMA at birth and timing of the neurobehavioral assessment.
- 4.2 The NaTI will be stopped for infants experiencing bradycardia, defined as HR less than 100 beats per minute for 10 seconds, or oxygen desaturation, defined as oxygen saturation less than 85% for 10 seconds. To prevent the overstimulation of infants during intervention delivery, the NaTI will be stopped for tachycardia, defined as HR greater than 200 beats per minute for 10 seconds. NaTI delivery may resume with the next planned intervention point in the care but will be discontinued for the remainder of the care for two or more episodes of bradycardia, oxygen desaturation, or tachycardia occurring during intervention delivery as defined above. A few infants may not tolerate the handling required to complete the neurobehavioral assessment. The Neurobehavioral Assessment of the Preterm Infant (**NAPI**) is intended to be administered in a specified, fixed sequence to minimize infant handling and potential distress. While we expect that infants at 35 weeks PMA will not find the assessment distressing, for those who exhibit signs of distress (e.g. bradycardia, oxygen desaturation, inconsolable crying), the assessment will be terminated.

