- **HPA axis activation.** Salivary cortisol will be measured from saliva samples taken immediately prior to the start of care (baseline), 30 minutes after the care has ended (post-care), and 60 minutes after the care has ended (recovery; Fig 2) using medical sponges gently introduced into the infant's mouth.. We have previously used these sponges for saliva collection from preterm infants without causing infant distress. A member of the research team, who is a Registered Nurse, will collect saliva samples with the assistance of the bedside nurse. Saliva collection is non-invasive and may be collected as part of clinical practice (test code XSCRT according to the NCH Laboratory Medicine website; see protocol Appendix). We will batch process samples and quantify cortisol levels using a commercially available enzyme-linked immunosorbent assay (**ELISA**; Salimetrics, State College, PA).
- **Recovery.** We will measure infant recovery by recording episodes of bradycardia, tachycardia, oxygen desaturation, or other monitor alarms during the 30-minute recovery period following the episode of essential nursing care. We will observe sleep behaviors to determine if the infant is awake, asleep, or drowsy during this 30-minutes recovery period using the Anderson Behavioral State Scale (ABBS). Behavioral data will be collected through observation without disturbing or handling the infant.
- **Context of care.** We will record the duration of the caregiving episode and the procedures included. We will use the acute scale of the Neonatal Infant Stressor Scale (**NISS**)⁸⁸ to quantify the procedural stressors experienced by infants during the observed care episode. We have previously modified this measure to account for

the procedural stressors commonly experienced by preterm infants⁷⁷. Additionally, we will observe and record all direct touches experienced by the infant for one hour prior to the caregiving episode. Direct touches are those defined as direct physical contact between a caregiver and infant and might include parent skin-to-skin care, interventions for apneic episodes, and adjustment of a respiratory interface. We will use these data to compare the context of care for infants between assigned conditions and will examine moderation of infant responses to care episodes by this context.

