We will collect biobehavioral data from infants. HR and HRV will be collected from monitoring equipment similar to that used as part of clinical care in the NICU. The collection of HR and HRV data will require the attachment of three additional ECG electrodes to the infant's chest. If the infant's chest is not large enough to accommodate the additional electrodes, electrodes for clinical monitoring can be moved to the infant's back at the nurse's discretion. The additional ECG electrodes may cause mild erythema after removal, similar to the removal of electrodes used for clinical monitoring. SCRs will require the attachment of two additional electrodes with isotonic gel to the infant's foot. These electrodes may cause mild erythema after removal, similar to the removal of electrocardiogram electrodes used for clinical monitoring. Salivary cortisol will be collected three times during the observation period (prior to the start of the care episode, 30 minutes after the care episode, 60 minutes after the care episode) using small medical swabs similar to those used to provide oral care to preterm infants. The swab will be gently introduced into the infant's mouth and held securely using the attached handle. There are no expected risks to infants from the saliva collection. Protected health information (PHI), including maternal prenatal data and infant clinical data, will be collected from each infant's EHR. There is a small risk of loss of confidentiality.

Nurse participants. Nurses will be asked to complete a demographic questionnaire once and an investigator-developed NaTI survey, the AIM⁹⁰, the IAM⁹⁰, and the FIM⁹⁰ each time they provide the NaTI to an infant. There is a small risk of loss of confidentiality for nurses who agree to participate. Surveys request nurse feedback on the intervention and will not include sensitive data.

- 15.2 As part of the biobehavioral data collection, there may be risks to infant participants that are not foreseeable.
- 15.3 If a pregnant nurse chooses to participant in the nursing survey study, there are no risks to her fetus.

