Interim Monitoring Procedures. On a monthly basis, the PI will produce interim reports specifically focusing on missing data and entry errors. The progress of the study will be monitored biannually by the college DSMC. On a biannual basis, the PI will prepare a written report on the progress of the study that will include data on: enrollment, comparison of target to actual enrollment, information on race, ethnicity, sex, overall status of the study participants, protocol deviations, and adverse or serious adverse events. These data will be collected in a spreadsheet format and reviewed by [name] (Study PI). All reports will be reviewed by the DSMC on a biannual basis. After each report is reviewed, the Committee will recommend whether the study should continue, continue with modifications, or be terminated. PI reports and minutes from DSMC meetings will also be sent to the Office of Responsible Research Practices. Co-I [name], who has extensive

experience with DSMCs and the conduct of clinical trials, will assist the PI in developing these reports.

Procedures for Adverse Events

Identification of adverse events. Study staff will be at the bedside during infant data collection and will record the occurrence of adverse events in real time. Adverse events (AEs) will be reported immediately to the PI. Adverse events may also be identified by parents or neonatal intensive care unit staff, who are encouraged to alert the PI of these events. During the consent process, participating nurses and parents of participating infants will be informed of the minimal risk nature of this study and encouraged to report any AEs immediately to study staff. The PI will maintain an electronic record of AEs and will include a description of AEs in the written report submitted biannually to the DSMC. Given the short-term duration of infant participation in the study, AEs will be tracked from the time that infant participation begins following the attachment of sensors for data collection and will continue until the end of the recovery period (i.e. 30 minutes after the final direct touch of the care episode).

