Definitions. **Adverse Event:** Any unfavorable and unintended sign, regardless of whether it is considered related to the intervention; also an “unanticipated problem” of any nature (e.g., psychological or social harm; designated as unrelated, definitely related, probably related, or possible related; see below). **Serious adverse event (SAE):** Any adverse event that is fatal or life threatening, is permanently disabling or requires prolongation of hospitalization. **Life-threatening event:** Any adverse event in which the subject is at immediate risk of death from the reaction as it occurs; does not include a reaction that, if it were to occur in a more serious form, might cause death. **Unexpected event:** Any adverse event that is not identified in nature, severity, or frequency in the study protocol or consent or the event was more serious than anticipated. **Definitely Related:** An adverse event that has a timely relationship to the administration of the investigational study procedure and follows a known pattern of response for which no alternative cause is present. **Probably Related:** An adverse event that has a timely relationship to the administration of the investigational study procedure and follows a known pattern of response, but for which a potential alternative cause may be present. **Possibly Related:** An adverse event that has a timely relationship to the administration of the investigational study procedure and follows no known pattern of response, but a potential alternative cause does not exist. **Unrelated:** An adverse event for which there is evidence that it is definitely related to a cause other than the investigational study procedure; in general no timely relationship to the administration of the procedure exists, or if so, the event does not follow a pattern of response and an alternative cause is present.

Grading scale for adverse event severity. **Mild:** Transient bradycardia (defined by clinical parameters established for each patient, usually heart rate <100 beats per minute), apnea, or oxygen desaturation requiring no intervention or an increase in supplemental oxygen. Bradycardia and oxygen desaturation are defined by clinical parameters established for each patient, usually heart rate <100 beats per minute or oxygen saturation <85% lasting 10 seconds. Erythema resulting from monitoring electrodes. **Moderate:** Bradycardia, apnea, or oxygen desaturation requiring an

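### The adverse-event window in section 18.1 closes about 2 hours before the study electrodes come off, so skin events that the plan anticipates and grades can fall outside it

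*Combined protocol and SAP*

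**What the plan says.** **Window.** Section 18.1 (Identification of adverse events) starts tracking once sensors are attached and states that it "will continue until the end of the recovery period (i.e. 30 minutes after the final direct touch of the care episode". Section 6.2 also gives the recovery period as 30 minutes.

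**Electrode removal.** Section 1.0 defines the observation period as "ending with the following scheduled care episode when electrodes are removed". Section 4.1 says that participation on each day "will end approximately 2.5 hours after the scheduled care episode", when the next care begins and the electrodes are taken off. Section 6.3 describes the study team removing them with moistened gauze to limit skin irritation.

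**Skin harms.** On the skin-conductance electrodes, section 15.1 says "These electrodes may cause mild erythema after removal"; it says much the same of the ECG electrodes. The severity scale in section 18.1 lists "Erythema resulting from monitoring electrodes" as mild and epidermal stripping from the electrodes as moderate.

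**Text pointing the other way.** Section 6.3 says, with no time limit, that every adverse event is to be recorded and reviewed. Section 18.1 has staff record events in real time at the bedside while data are being collected, and encourages parents and unit staff to report. Section 4.1 adds "Data collection to accomplish aims 1 & 2 will last the duration of two observation periods".

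**The concern.** The plan gives two end points for capturing adverse events. Someone who follows the window sentence stops about 30 minutes into a wait of about 2.5 hours, and may leave out a skin lesion first seen when an electrode is lifted. Someone who follows section 6.3 records the same lesion. The skin-event count in the twice-yearly report to the Data Safety Monitoring Committee (DSMC) then depends on which sentence that person had in mind.

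Electrode skin injury is one of the few harms that the plan names for its own research procedures. Expedited review by the committee chair of events judged related also depends on the event being recorded first.

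**Working it through.** This is timeline arithmetic; no power or error-rate formula applies.

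**Inputs**
- Attachment to start of care: about 3 h (section 4.1).
- Care to removal: about 2.5 h (section 4.1).
- Attachment to removal: about 6 h (sections 1.0 and 9.1).
- End of care to window close: 0.5 h (section 18.1), taking the final touch as the end of care.
- Care duration *d*: not given in the documents. I assume 0.25 to 1.0 h.

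**Reproducing the 6 h.** 3 + *d* + 2.5 = 6 gives *d* = 0.5 h, so the stated figures agree with each other if care lasts about half an hour.

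**Timeline with d = 0.5 h**, counted from attachment: care starts at 3.0 h and ends at 3.5 h; the window closes at 3.5 + 0.5 = 4.0 h; electrodes come off at 6.0 h. The gap is 6.0 − 4.0 = 2.0 h, one third of the observation period (2/6).

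**Sensitivity of the gap**

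| Reading | Formula | d = 0.25 | d = 0.5 | d = 0.75 | d = 1.0 |
|---|---|---|---|---|---|
| 2.5 h runs from end of care | 2.5 − 0.5 | 2.0 | 2.0 | 2.0 | 2.0 |
| 2.5 h runs from start of care | 2.5 − d − 0.5 | 1.75 | 1.5 | 1.25 | 1.0 |
| Total fixed at 6 h | 6 − 3 − d − 0.5 | 2.25 | 2.0 | 1.75 | 1.5 |

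The gap is positive in every cell and ranges from 1.0 to 2.25 h.

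**Which removals fall outside.** The text does not say whether tracking restarts on day 2.
- One continuous span across both days: day-1 removal is covered and last-day removal is not. For up to 20 infants, 20 × 1 = 20 removals are outside; for the 16 with complete data, 16.
- Daily restart: both removals are outside, 20 × 2 = 40, or 16 × 2 = 32.

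These counts are occasions on which an event could go unrecorded. They are not events.

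**Does other text move the end point?** The statement in section 6.3 is general, whereas the window sentence is specific about timing. Section 4.1 says data collection spans the observation periods but also labels the care episode itself the data collection period, so bedside recording can be read as ending with care or as reaching removal. Reports from parents and unit staff are encouraged but not scheduled. Nothing in the text reviewed calls for a skin check at removal.

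**The case against.** The best defence is that the plan plainly intends to record these events. They are in the severity scale, section 6.3 asks for every event, the study team takes the electrodes off itself, and others are invited to report. The Infant Data Form is not in the text reviewed and may already have a skin entry. Mild erythema is likened in section 15.1 to what clinical electrodes cause. A lasting day-1 lesion could also be seen when electrodes are reattached on day 2. All of this stands and limits the practical risk. It does not change the window sentence, and it gives no cover for last-day removal.

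Stronger readings are tempting, but the documents do not carry them:
- *Events will be missed.* A reader might infer this from the removal counts. The documents give no event rate, and the mitigating text may capture some or all events.
- *The plan expects skin injury at removal.* Section 15.1 says only that erythema may occur, and the severity scale does not mention removal. The link comes from sections 6.3 and 15.1.
- *The saliva sample is also exposed.* Section 6.2 places the last sample "60 minutes after the care has ended (recovery; Fig 2", after the window closes. But that is a label for a cortisol time point, a research nurse takes the sample, and section 15.1 expects no risk from it. It adds no named harm.
- *The gap could exceed 3 hours.* Section 3.1 describes care as "typically occurring every 3 or 4 hours during the infant's hospitalization", and a 4-hour interval would give 4 − 0.25 − 0.5 = 3.25 h. That sentence is background on usual practice and does not fit the 3 h, 2.5 h and 6 h of this study.
- *The treatment comparison is biased.* The same electrodes are worn under both conditions, and AE counts do not enter the primary analysis.

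**Conclusion.** The point holds as an internal conflict in the safety plan. Followed as written, section 18.1 stops tracking about 2 h before electrode removal and so excludes skin events, named and graded by the plan itself, that first appear at or after removal. This affects at least the last-day removal for every infant, and both removals if tracking restarts daily.

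The 2 h figure rests on the plan's own approximate times. The range of about 1 to 2.25 h rests on an assumed care duration of 0.25 to 1.0 h and on whether the 2.5 h is counted from the start or the end of care. Confidence is high that the passages disagree. Whether any event would actually be lost cannot be judged from the documents. The consequence is limited to safety capture, but the correction is cheap enough that it should be made.

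**What to change.** Reconcile section 18.1 with sections 1.0, 4.1, 6.3 and 15.1:

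1. Amend the window sentence so that, at least for electrode-related skin events, tracking on each observation day runs through electrode removal and a skin check immediately afterwards. The check is needed because section 15.1 places erythema after removal; a window that ended at the act of removal could still miss it.
2. State whether tracking is continuous across the two days or restarts, and word the change so that it does not shorten any between-day coverage that the current text gives.
3. Record skin condition at that check as one entry on an existing form, if it is not already there.

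The cost is one or two sentences and at most one form entry, completed at a removal that the study team already performs. A few more mild events may be recorded; the documents give no rate from which to estimate how many. If the window is widened for all events and not only skin events, it grows from about 4 h to about 6 h per day, and part of the added time would rely on unit-staff reporting while study staff are away from the bedside. Limiting the extension to skin events avoids that uneven ascertainment.

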6.2 **Procedures. Aims 1.** Infants will be enrolled during the first 10 days of life. We will collect demographic and clinical data from the infant's electronic health record (**EHR**) after enrollment and throughout the hospitalization. Because stress responses may differ based on postnatal age⁸¹, data collection for stress responses will occur between 10 and 20 days of life. To eliminate variance in cortisol due to diurnal patterns, we will perform all observations at the same time of day for all infants, between 1000 and 1300. Observations will occur on two consecutive days unless infants are not available due to off-unit or other scheduled procedures. In this case, the second observation will occur on the next day that the infant is available. Infants will be assigned to receive standard care or standard care with a NaTI in a randomly assigned sequence. For the two observed care episodes, we will require that nurses provide this care exclusively to limit confounding by the participation of additional caregivers. With assistance from the bedside nurse, the researcher, who is a Registered Nurse, will attach monitoring electrodes for vital signs, HRV, and SCRs during the care episode prior to the observed care to minimize stress responses from handling and monitoring prior to the baseline period (Fig 2). Nurses commonly attach monitoring electrodes as part of their clinical practice.

[figure not shown]

Figure 2. Timeline of study measures.

Measures, Aims 1:

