For the safe delivery of the NaTI, we have developed specific criteria to determine when the intervention should be stopped. The NaTI will be stopped for infants experiencing bradycardia, defined as HR less than 100 beats per minute for 10 seconds, or oxygen desaturation, defined as oxygen saturation less than 85% for 10 seconds. To prevent the overstimulation of infants during intervention delivery, the NaTI will be stopped for tachycardia, defined as HR greater than 200 beats per minute for 10 seconds. NaTI delivery may resume with the next planned intervention point in the care but will be discontinued for the remainder of the care for two or more episodes of bradycardia, oxygen desaturation, or tachycardia occurring during intervention delivery as defined above. Additionally, nurses will provide clinical interventions, including increasing supplemental oxygen, based on their clinical judgement. All adverse events will be recorded and reviewed to determine expectedness, relatedness, and severity.

Nurse participants. We will protect the confidentiality of data for nursing surveys by assigning each participating nurse a SID that will be used to label all data. The key linking nurse identities to SID will be encrypted and stored on an electronic password-protected encrypted research server at the CON. The key linking names and SIDs, electronic and paper data forms, and consent forms will be stored in separate locations. Electronic access to the research server is restricted to the OSU CON local area network or virtual private network by a Cisco ASA 5510 firewall. Paper data forms and consent forms will be stored in locked filing cabinets in a

PROTOCOL TITLE: Pilot Study of Nurse-Administered Touch and Biobehavioral Stress Responses of Preterm Infants (Pilot NAT-BIO Study)

locked office in the OSU CON. Access to the key, data, and consent forms will be limited to research team members who have been approved by the IRB and are compliant with all required training in the protection of human subjects. Surveys will request nurse feedback on the intervention and will not include sensitive data. Nurses always have the option to skip questions that they do not wish to answer.

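### The adverse-event window in Section 18.1 closes before the NAPI session, so the plan does not require events during that session to be tracked, graded or sent to the DSMC

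*Combined protocol and SAP*

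**What the plan says.** The AE window is set in Section 18.1, under identification of adverse events. It opens on the observation day: "AEs will be tracked from the time that infant participation begins following the attachment of sensors for data collection". It closes the same day, because tracking "will continue until the end of the recovery period (i.e. 30 minutes after the final direct touch of the care episode". The reason given is "Given the short-term duration of infant participation in the study".

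Other sections describe a longer involvement. Section 1.0 says "Total infant participation will last from the time of the first observation to neurobehavioral assessment", and Section 4.1 says "Infant participation for the entire study will last between 5-7 weeks". The assessment that ends participation is the NAPI. It is planned for every enrolled infant at about 35 weeks PMA (Sections 6.1 and 6.2), lasts 20-30 minutes (Section 1.0), and is listed as a research activity in Table 1 of Section 6.4.

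Section 4.2 allows that a few infants may not tolerate the NAPI handling, and adds that the team expects infants at 35 weeks not to be distressed by it. It then says that "for those who exhibit signs of distress (e.g. bradycardia, oxygen desaturation, inconsolable crying), the assessment will be terminated". No recording, grading or reporting step follows.

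Section 6.3 contains a general sentence: "All adverse events will be recorded and reviewed to determine expectedness, relatedness, and severity".

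**The concern.** The NAPI is handling done for research, and the protocol itself names the events that might end it. Two of these, bradycardia and oxygen desaturation, are graded AEs elsewhere in Section 18.1. During an observed care episode the same events would be logged, graded and reviewed. During the NAPI no rule clearly requires this.

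The DSMC makes its recommendation to continue, modify or terminate from the reports it receives. If NAPI events are not in those reports, the committee cannot see a tolerance problem with that procedure. Separately, Aim 3 uses the NAPI scores, and Section 17.1 does not say how assessments stopped early are to be accounted for.

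**Working it through.** The plan gives no figure to reproduce here. The check is a reading of the AE rule against the study timeline, with some date arithmetic.

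**Inputs**
- PMA at birth: 27-30 weeks (Section 10.2).
- Observed care: "data collection for stress responses will occur between 10 and 20 days of life" (Section 6.2).
- NAPI: about 35 weeks PMA, earlier if discharge is anticipated, later if the infant is not stable (Section 6.2).
- Sessions: up to 20 infants, 20-30 minutes each (Section 1.0).

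**Gap between the close of the window and a NAPI at 35w0d**

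Gap = 35w0d − (PMA at birth + day of life at observation), with 35w0d = 245 days.

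| Born | Observed on day | PMA at observation | Gap |
|---|---|---|---|
| 27w0d (189 d) | 10 | 28w3d (199 d) | 245 − 199 = 46 days |
| 30w0d (210 d) | 20 | 32w6d (230 d) | 245 − 230 = 15 days |
| 30w6d (216 d), if 30 weeks includes it | 20 | 33w5d (236 d) | 245 − 236 = 9 days |

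The range is 9 to 46 days. Counting from a second observation one day later would reduce the 46 to 45. A NAPI at 35 weeks therefore always falls after the window has closed. A NAPI brought forward before discharge would still be a separate session: as described, it involves no study sensors and is not a care episode, so neither end of the window applies to it.

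**Exposure outside the required window**

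20 × 20 min = 400 min = 6.7 hours, and 20 × 30 min = 600 min = 10 hours.

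**Is it only the window that excludes these events?**
- The AE definition in Section 18.1 covers unfavorable, unintended signs whether or not the intervention caused them, so NAPI events qualify.
- The severity scale in Section 18.1 grades bradycardia, apnea and desaturation. It has no entry for inconsolable crying.
- Section 15.1, on infant risks, does not mention NAPI handling.

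For bradycardia and desaturation, then, the window is the only obstacle. For inconsolable crying a grade is missing as well.

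**Does the rationale fit?** Section 18.1 relies on short participation, whereas Section 4.1 gives 5-7 weeks. The short-duration argument describes the observation days, not the whole of participation.

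**The case against.** The best opposing case is that other text already covers the NAPI. Section 18.1 has staff record AEs in real time during infant data collection, and Table 1 lists the NAPI among the infant data items. Parents and unit staff are encouraged to report AEs, with no time limit in that sentence. The Section 6.3 sentence refers to all adverse events. This has some force: a reader might infer from the window that NAPI events will never be recorded, and the documents do not show that. Staff could record them under these sentences. But none of them names the NAPI. Section 4.1 uses the data-collection label for the care episode, alerts from parents and staff are passive, and the Section 6.3 sentence closes a paragraph about safe delivery of the NaTI. Coverage is left ambiguous, and the one explicit time limit points the other way.

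A second argument is that Section 18.1 aims its safety plan at data related to the intervention, and that the NAPI, given after both crossover conditions, cannot inform a comparison of NaTI with standard care. That is true of the comparison. It does not explain why a research procedure with named stopping signs should have no clear recording rule.

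Third, Section 4.2 should not be read as predicting intolerance. It says that a few infants may not tolerate the handling and expects no distress at 35 weeks. The fixed sequence and the delay for unstable infants are further safeguards. All of this stands, and it limits the likely number of events.

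Finally, a reader might infer that Aim 3 would lose its most reactive infants without a documented reason. The documents do not support that. The study forms are not in the text available, the monthly reports address missing data, and Aim 3 is exploratory.

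**Conclusion.** The point holds as a gap in a stated rule. Followed as written, the AE window closes before the NAPI, by about 9 to 46 days for an assessment at 35w0d, and nothing else clearly requires NAPI events to be tracked, graded or sent to the DSMC. Up to 20 sessions, 6.7 to 10 infant-hours, are affected.

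The day range assumes a NAPI at exactly 35w0d and observations within days 10-20. The lower end also assumes that 30 weeks includes 30w6d. The number of sessions that would be stopped is unknown, and no bias in the Aim 3 results is claimed. In a minimal-risk pilot this is a modest issue, but it should be corrected because the protocol itself names the events and closing the gap costs very little.

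**What to change.** In Section 18.1, add a second AE recording window for the NAPI session, from first handling to its end, using the existing AE definitions, severity grades and DSMC route. State how distress that has no current grade, namely inconsolable crying, is to be recorded. Correct the short-participation rationale, and make the general sentences in Sections 6.3 and 18.1 agree with the windows. Record each terminated NAPI with its reason, and report the count with the Aim 3 results.

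The criteria for ending the assessment are not affected. The cost is two or three sentences and one line on the NAPI form, with no added staff because the examiner is already present.
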